3.3 Study Duration and Dates

This is a phase 1, two-period, two-treatment, crossover study. Subjects will be screened within 28 days of the initiation of study drug dosing. Eligible subjects who consent to the study will be randomly assigned to 1 of 2 groups, each group will receive both treatments alternately, in a crossover fashion (two-period, two-treatment crossover design), with the two treatment periods separated by a 7-day washout period.

In treatment period 1, subjects will be admitted to the clinic on day 0, the day before dosing, and will stay in the clinic until 48 h post-dose. In treatment period 2, subjects will be admitted to the clinic on day 7, the day before dosing, and will stay in the clinic until 48 h post-dose. The scheduled visits and procedures for each visit are provided in [Appendix 1](#).

4 STUDY POPULATION SELECTION

4.1 Study Population

Eighteen eligible healthy subjects who consent to participate in this study will be enrolled.

4.2 Inclusion Criteria

Each subject must meet the following criteria to be enrolled in this study.

1. Subjects who are between 18-65 years of age inclusive with body-mass index (BMI) between 18.0 kg/m² and 32.0 kg/m², inclusive.
2. Male subjects who are surgically sterile or male subjects who are not surgically sterile must agree to refrain from donating sperm and use appropriate birth control such as the use of condoms when engaging in sexual intercourse for a period of 30 days after discharge from the clinic.
3. Female subjects of childbearing potential who are willing to use an adequate method of contraception and to not become pregnant for the duration of the study.
4. Female subjects who are surgically sterile (hysterectomy, oophorectomy) or postmenopausal (absence of menses greater than 12 months and age > 45 years) are eligible if they test negative on the urine pregnancy test.
5. Subjects who are non-smokers for at least 3 months prior to screening.
6. Subjects with adequate venous access at multiple sites in both arms.
7. Subjects who are willing and able to be confined to the clinical research facility as required by the protocol.
8. Subjects who have the ability to comprehend and willingness to provide written informed consent in accordance with institutional and regulatory guidelines.

4.3 Exclusion Criteria

Subjects who meet any of the following criteria will be excluded from the study.

1. Subjects who are determined by the investigator or sub-investigator to be unsuitable for participating in the study based on medical conditions, including impairment of the central nervous system, circulatory system, respiratory system, blood/hematopoietic function system, gastrointestinal system, liver/kidney function, thyroid function, pituitary function and/or adrenal function.
2. Female subjects who are nursing or pregnant.
3. Subjects with a clinically significant history of allergy to drugs or latex.
4. Subjects with a history of alcohol or drug dependence in the last 12 months.
5. Subjects who had 400 mL of whole blood collected within four months or 200 mL of whole blood collected within one month of the screening test.
6. Subjects who had blood component collection within 14 days prior to the screening test.
7. Subjects who have used prescription or over-the-counter (OTC) drugs within 14 days prior to the first dose.

8. Subjects who have used vitamin preparations or supplements (including St. John's Wort and ginseng) within 14 days prior to the first dose.
9. Subjects who have undergone strenuous activity within 72 hours prior to Day 1 in each period.
10. Subjects who are unable (e.g., food intolerance) or unwilling to consume a high-fat breakfast within 25 minutes.
11. Subjects who have been treated with an investigational drug within 30 days or 7 half-lives of the investigational drug, whichever is longer, prior to the first dose of study drug in this trial.
12. Subjects who had previously received EGT0001474 or bexagliflozin, or any other SGLT2 inhibitors within 3 months from the screening.
13. Subjects whose screening electrocardiogram (ECG) demonstrates any one of the following: heart rate > 100 bpm, QRS > 120 msec, QTc > 470 msec (corrected by Bazett's formula), PR > 220 msec (a subject with PR > 220 msec will generally be excluded but exceptions may be allowed at the discretion of the investigator), or any rhythm that is not sinus rhythm, sinus bradycardia, or sinus arrhythmia.
14. Subjects whose sitting blood pressure is above 140/90 mmHg at screening.
15. Subjects who have a positive result of HBsAg antigen, HCV antibody, urinary drug or urinary cotinine test.
16. Subjects with known human immunodeficiency virus (HIV) disease.
17. Subjects with abnormal vital signs, laboratory values, symptoms or signs that are deemed clinically significant by the investigator.
18. Subjects who have had a febrile illness within 5 days prior to the first dose of study medication.
19. Subjects vaccinated within 30 days prior to the first dose of medication.
20. Detectable urine glucose at screening (trace or greater).
21. Subjects with eGFR < 90 mL/min/1.73 m² or a history of kidney transplant.
22. Subjects with digestion problems, including gastroesophageal reflux disease, irritable bowel syndrome, gastroparesis, and any other disorder deemed by the investigator to be clinically significant.

5 STUDY TREATMENTS

5.1 Study Drug

Bexagliflozin tablets, 20 mg, are blue caplet-shaped, film-coated tablets that are intended for use in investigational studies in humans. The tablets contain excipients designed to promote extended release through a gastroretentive mechanism. The active tablets exhibit a greater than 75% release of drug substance by 8 hours in simulated gastric fluid *in vitro*.

5.2 Treatments Administered

Subjects who consent to be in the study will be randomly assigned to 1 of 2 treatment groups. Each group will be dosed with bexagliflozin under a fasted state in one period and under a fed state (high fat, high calorie) in the other period. A single oral dose of bexagliflozin tablets, 20 mg, will be provided to subjects in each treatment period.

The detailed dosing schedule is shown in Table 1.

Table 1. Dosing Schedule

Subject Group	Treatment Period	Treatment Period 1 (Day 1)			Treatment Period 2 (Day 8)		
		Dosing Time (h)	-0.5	0	4	-0.5	0
Group 1	Bexagliflozin single oral dose		X			X	
	*Meal	X		X			X
Group 2	Bexagliflozin single oral dose		X			X	
	*Meal			X	X		X

*High-fat meal will be provided at time -0.5 h, while standard meal will be provided at other times.

5.3 Selection and Timing of Dose for Each Subject

Dosing order with bexagliflozin alone or in combination with food will be based on randomized assignment. Results from previous clinical trials indicate that doses of 1.7 mg to 100 mg of bexagliflozin are well tolerated and the planned dose of bexagliflozin tablets, 20 mg, produced significant glucosuria and is not expected to produce serious drug-related adverse events.

- **Bexagliflozin alone:** After an overnight fast of at least 10 h, a bexagliflozin tablets, 20 mg, will be administered 4 h prior to the first meal of the day with 240 mL of water.
- **Co-administration of bexagliflozin with food:** After an overnight fast of at least 10 h, a bexagliflozin tablets, 20 mg, will be administered 30 min after starting to consume a high-fat meal with 240 mL water.

If for some reason, a portion of the water is not consumed, the reason and the amount of remaining water will be recorded.

5.4 Method of Assigning Subjects to Treatment Groups

A sufficient number of subjects will be screened to ensure that up to 18 subjects will be randomized. Eligible subjects will be randomly assigned to group 1 or group 2 in a 1:1 ratio. Subjects who discontinue the study after randomization for non-safety related reasons may be replaced to ensure that the number of evaluable subjects in each group should not be less than 8.

5.5 Blinding

This is an open-label study. There is no blinding process in this protocol.

5.6 Concomitant Therapy

The participants are not allowed to take any prescription or non-prescription drugs, vitamins, or dietary supplements at any time during 14 days prior to (first) drug administration and for the duration of each study period. No other concomitant medications are permitted with the exception of those required for treatment of an adverse event. Subjects may receive any medications for adverse events that are necessary to control or minimize the likelihood of more serious adverse events in the investigators' judgment.

Concomitant medications administered at the time of randomization and during the study are to be recorded on the case report form (CRF). The medication name, dose, frequency, route of administration, date(s) of administration and reason for administration must be recorded. This documentation should continue until 1 week from the end of the last study product dosing. Medications that a subject receives after entering the study and prior to randomization must be recorded in the CRF.

5.7 Restrictions

5.7.1 Prior Therapy

No study subject shall have been dosed with any SGLT2 inhibitor within 3 months prior to the screening, nor an investigational drug within 30 days or 7 half-lives, or used any prescription medication or herbal supplements within 14 days prior to the first dose of study medication.

5.7.2 Fluid and Food Intake

An overnight fast of at least 10 h prior to dosing is required. For the fasting state treatment group, oral intake of food (standard meals) will be restricted for 4 h following administration of bexagliflozin.

The fed state treatment will consist of a bexagliflozin tablet, 20 mg, taken 30 min after subjects start to consume a high-fat (approximately 50% of total caloric content of the meal), high-calorie (approximately 800–1000 cal) meal after an overnight fast.

Each dose will be administered with 240 mL tap water. Food intake will be forbidden during the first 4 h post dosing. Water can be allowed as desired except for one hour before and after drug administration

Subjects are expected to consume 100% of the high-fat meal and 240 mL of water provided. If a portion of the meal and water is not consumed, the reason and the amount of remaining meal and water will be recorded.

Subjects should receive standard meals scheduled at the same time in each period of the study.

5.7.3 Subject Activity Restrictions

Light physical activity is permitted. Subjects should not perform strenuous activity during the clinical stay and during the washout period as this could result in elevations of muscle creatinine kinase (CK) levels. Smoking during the study is prohibited.

5.8 Treatment Compliance

To ensure compliance, all medication dosing will be supervised by the Investigator or qualified staff in the clinic. The exact times of medication dosing will be recorded in the CRFs, including a record of checks followed by hand mouth inspection.

5.9 Packaging and Labeling

Investigational product will be provided to the pharmacist or designated site personnel in bottles of 90 tablets enclosed with a child-resistant cap. The pharmacist or designated site personnel will dispense the investigational products for each subject according to randomization assignment.

5.10 Storage and Accountability

Bexagliflozin tablets should be stored at controlled room temperature, 15 to 30°C (59 to 86°F) in a secure area with access limited to authorized personnel. The drug storage facility must comply with the medication storage instructions. The trial staff must record the amount of investigational product dispensed to each subject in the dosing record. A full reconciliation of drug inventory will be performed at the end of the study and the results of this inventory must be recorded in the Drug Accountability Form. All unused drug must be returned to a sponsor-designated depot after drug accounting is verified by the sponsor or its designee.

6 STUDY PROCEDURES

6.1 Informed Consent

Before each subject is enrolled in the clinical study, written informed consent will be obtained from the subjects according to the regulatory and legal requirements. As part of this procedure, the investigator or designee must explain orally and in writing the nature, duration, and purpose of the study, and the action of the drug in such a manner that the study subject is aware of the potential risks, inconveniences, or AEs that may occur. The investigator should educate potential subjects about the scientific importance of their data and the vital role that their participation has for the outcome of the entire study. The subject must be informed that he/she is free to withdraw from the study at any time. He/She will receive all information that is required by federal regulations and International Conference on Harmonisation (ICH) guidelines.

The informed consent document must be signed and dated; one copy will be given to the subjects, and the investigator will retain a copy as part of the clinical study records. The investigator will not undertake any investigation specifically required for the clinical study until written consent has been obtained. The terms of the consent and when it was obtained must also be documented.

6.2 Medical History

The following information will be collected at the screening visit:

- Demographic information including age, sex, and race and whether childbearing potential if female.
- Significant medical, surgical history and timeframe of the history relative to study screening, if applicable.
- Clinically significant history of allergy including drugs and latex.
- History of smoking, alcohol or drug dependence, or abuse in the last 12 months.
- Any blood donation or blood component donation within 4 months.
- Use of any medications including over the counter drugs, vitamins, or dietary supplements within 14 days.
- History of vaccination within 30 days prior to the first dose of study medication.
- History of diagnosis with HIV, hepatitis B or hepatitis C.
- Use of any investigational drug in the previous 30 days or 7 half-lives, whichever is longer.
- Prior exposure to bexagliflozin (or EGT0001474), or any other SGLT2 inhibitors within 3 months from the screening.

6.3 Physical Examination

The investigator or designated qualified individual will perform the physical examinations (PEs). A complete physical examination will be performed at screening and at the termination visit. Partial physical examinations will be performed at scheduled visits.

A complete physical examination will include measurement of body weight and height (height will be measured only at screening), general assessment of all body systems including the skin, head, eyes, ears, nose, throat, neck, lungs, heart, abdomen, lymph nodes, and extremities. A partial physical examination will include body weight and an update of the general assessment of the skin, heart, lungs and abdomen.

6.4 Vital Signs

Vitals signs, including pulse, systolic and diastolic blood pressure (BP) in a seated position will be obtained after a subject has been sitting for 5 min, respiration rate (RR), and oral temperature, will be measured at the scheduled visits described in [Appendix 1](#). BP measures will be obtained using a calibrated sphygmomanometer.

Vital signs should be measured prior to blood draws.

Respiration rate should be measured after at least 5 min of rest. Devices designed to measure BP from the finger or wrist may not be used.

6.5 Electrocardiography and Continuous Telemetry Monitoring

6.5.1 12-Lead Electrocardiograms

A 12-lead electrocardiogram (ECG) will be conducted as listed in [Appendix 1](#) and whenever clinically indicated.

This procedure should be performed in the supine position after at least 10 min of rest. ECG parameters measured will be the RR interval, PR interval, QRS duration, and QT. Each ECG should also be assessed by the investigator for signs of ischemia, clinically significant hypertrophy, and clinically significant T-wave abnormalities.

It is the investigator or designee's responsibility to review the results of the ECG as they become available. For each abnormal ECG result, the investigator needs to ascertain if this is a clinically significant change from the screening ECG for that individual subject (this determination, however, does not necessarily need to be made the first time an abnormal result is observed. The investigator may repeat the ECG to verify the results of the original result). If the ECG result is determined to be a clinically significant and abnormal change from baseline for that subject, this is considered an AE.

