7.3 Day 1 Activities (Pre-dose)

The following information will be gathered and the indicated procedures will be performed Pre-dose:

- Record vital signs pre-dose.
- Perform 12-lead ECG taken in the supine position after at least 10 min of rest pre-dose.
- Complete pre-dose urine collection at 0 h (-12 h to 0 h) for baseline UGE analysis and analysis of electrolytes, uric acid and creatinine analysis as described in [Section 6.6.2.3](#).
- Urine sample will be prepared for pre-dose urinalysis as described in [Section 6.6.2.2](#). If urine is dipstick positive for leukocyte esterase or nitrites, sample is to be sent for microscopic evaluation and culture.
- Pre-dose blood will be drawn for hematology, and serum chemistry as detailed in [Section 6.6.2.1](#).
- Pre-dose plasma samples will be drawn for PK analysis as detailed in [Section 6.6.2.4](#).
- Pre-dose concomitant medications and adverse event information collected as appropriate.

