Appendix 1 Schedule of Events

[figure not shown]
Study activity	Screening		Period 1					Period 2			
	D -28 to -1	D0	D1 pre-dose	D1 post-dose	D2	D3	D7	D8 pre-dose	D8 post-dose	D9	D10
Medical history and ICF	X										
Screening for I/E criteria ¹	X	X					X				
Physical exam ²	X	X									X
Demographics	X										
Randomization		X									
Admission and discharge		X				X	X				X
Vital signs ³	X		X	X	X	X		X	X		X
ECG ⁴	X		X	X				X	X		X
Urinalysis ⁵	X		X			X		X			X
Blood draw for clinical lab tests ⁶	X		X			X		X			X
Blood sample for PK ⁷			X	X	X	X		X	X	X	X
Urine Collection ⁸		X	X	X	X	X	X	X	X	X	X
Urine Pregnancy Test	X										
Adverse event and concomitant medication		X	X	X	X	X	X	X	X	X	X
Study termination											X

[figure not shown]
1. Subject compliance with inclusion and exclusion criteria will be verified at check-in of each period (on day 0 and day 7).
2. Weight and height will be recorded as part of the physical examination. Height will be recorded once at screening only. A complete physical exam (PE) will be performed at screening and day 10 prior to discharge.
3. Vital signs include: pulse, body temperature, respiration rate, systolic and diastolic blood pressure. On days 1 and 8, vital signs will be determined at pre-dose and at 4 h and 48 h (day 3 or 10) post-dose.
4. 12-lead ECG will be conducted after 10 min of rest. ECG data will be recorded at screening, on days 1 and 8 at pre-dose and at 4 h post-dose and when clinically indicated.
5. Clean sample to be collected at each visit. If urine is dipstick positive for leukocyte esterase or nitrites, sample is to be sent for microscopic evaluation and culture. Urine drug screen will be performed on screening visit only. If screening is conducted more than 5 days prior to dosing, drug screening shall be repeated.
6. Blood samples at the designated visits for clinical chemistry and hematology parameters are listed in [Table 2](#).
7. Plasma samples for the PK profile of bexagliflozin will be collected at pre-dose and at 1, 2, 3, 4, 5, 6, 8, 10, 12, 16, 24, 36, and 48 h post-dose.
8. Urine collection for urinary glucose (PD), electrolytes, uric acid & creatinine are described in Section 6.6.2.3.

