### **6.3.3.1 Treatment-Emergent AE (TEAE)**

An adverse event is considered treatment-emergent if the date of onset is on or after the date of first dose of study medication, or worsens during the treatment period (intensity/severity grades worsen).

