### **6.3.6 Electrocardiogram**

ECG parameters, including the RR interval (intra-beat interval), PR interval (the period that extends from the beginning of the P wave [the onset of atrial depolarization] until the beginning of the QRS complex [the onset of ventricular depolarization]), QRS duration, and QT interval (the corrected QT interval is the measure of the time between the start of the Q wave and the end of the T wave in the heart's electrical cycle), will be measured according to the study assessment schedule as specified in Section 3.6. Each ECG will be assessed by the Investigator for signs of ischemia, clinically significant hypertrophy, and clinically significant T-wave (repolarization of the ventricles) abnormalities. Baseline ECGs will be defined as the last evaluation performed prior to the administration of study drug in each treatment period.

ECG changes from baseline will be summarized by treatment.

Change from baseline to time point t, denoted  $\text{Change}_t$ , will be calculated as:

$$\text{Change}_t = \text{Value}_t - \text{Value}_{\text{Baseline}}$$

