## **8.4 Safety Analyses**

Safety analyses will be performed using the Safety Population, unless otherwise specified.

Safety measurements will include AEs, clinical laboratory tests (i.e. serum chemistry, hematology and urinalysis), ECGs, physical exams and vital signs. All safety data will be summarized by treatment. Baseline values for clinical laboratory tests, vital signs and ECGs will be defined as the last evaluation performed prior to administration of study drug.

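### Protocol 6.5.1 names two different comparators for calling an ECG an adverse event, and the protocol and SAP disagree on whether a Day 1 pre-dose finding is treatment-emergent

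*Protocol*

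**What the plan says.** Protocol 6.5.1 deals with abnormal ECGs in two steps. In the first, "the investigator needs to ascertain if this is a clinically significant change from the screening ECG for that individual subject". In the second, "If the ECG result is determined to be a clinically significant and abnormal change from baseline for that subject, this is considered an AE". The first step names the screening tracing. The second names baseline, and the protocol does not say which ECG that is.

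The SAP does say. In Section 6.3.6, "Baseline ECGs will be defined as the last evaluation performed prior to the administration of study drug in each treatment period". Section 8.4 is less specific: "Baseline values for clinical laboratory tests, vital signs and ECGs will be defined as the last evaluation performed prior to administration of study drug". SAP Appendix 1 likewise leaves out the period.

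On timing, footnote 4 to the protocol's Schedule of Events states: "ECG data will be recorded at screening, on days 1 and 8 at pre-dose and at 4 h post-dose and when clinically indicated". The schedule grid and Protocol 7.7 add an ECG on Day 10. Each period therefore has its own pre-dose tracing.

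On emergence, SAP 6.3.3.1 counts an event as treatment-emergent "if the date of onset is on or after the date of first dose of study medication", or if it worsens during treatment. Protocol 9.6.1 starts the clock at administration of the drug. Both documents assign an event to the first treatment when its onset falls after the first dose and before the second, and both tabulate only treatment-emergent events.

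**The concern.** The investigator decides at the site, from the protocol, whether an ECG is an adverse event. The SAP's baseline definition governs later tables and cannot undo an event already recorded. If the investigator follows the first step of 6.5.1, the reference is a tracing that may be several weeks old, although a pre-dose ECG from the same morning is available.

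The parallel laboratory rule in Protocol 6.9 uses baseline in both of its steps, so the ECG paragraph is the exception. Safety in the fasted and fed states is a secondary objective, and treatment-emergent events are tabulated by treatment. At stake is whether ECG events in that table mean a change since dosing or a change since screening.

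**Working it through.** The plan gives no figure to reproduce. The check sets the rules side by side and applies them to the scheduled ECGs.

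**Age of the screening ECG.** Screening runs from Day -28 to Day -1, and the schedule has a Day 0. By day numbering, the longest gap is 1 - (-28) = 29 days to dose 1 and 8 - (-28) = 36 days to dose 2.

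**The two comparators, case by case.**

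| Case | Against screening | Against SAP 6.3.6 baseline | Result |
|---|---|---|---|
| A. 4 h ECG same as pre-dose, different from screening | change | no change | event under the screening wording only |
| B. Abnormal at screening, normal pre-dose, abnormal post-dose as at screening | no change | change | event under the baseline wording only; can be missed |
| C. Day 1 pre-dose abnormal, screening normal | change | is itself the baseline (change = 0) | can be recorded as an event; emergence depends on the document |
| D. Day 8 pre-dose newly abnormal | change | is itself the Period 2 baseline | a proper event with onset after dose 1, assigned to the Period 1 treatment |
| E. Change arises after dose 1 and persists unchanged at 4 h after dose 2 | change | no change from Day 8 pre-dose | one ongoing event with Period 1 onset |

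A and B show that the comparators conflict in both directions. Case B should be the rarer, because exclusion criteria 13 and 17 remove subjects with listed or clinically significant screening abnormalities.

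**Emergence in case C.**

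- SAP 6.3.3.1: the onset date equals the first-dose date, so the finding is treatment-emergent.
- Protocol 9.6.1: onset precedes administration, so it is not emergent.
- SAP 6.3.3: by onset time it does not follow the first dose, so it belongs to neither treatment.

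Under the SAP the finding is thus emergent but has no treatment column. If only a date is recorded, the assignment rule does not settle the matter.

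**Size.** Only the Day 1 pre-dose ECG precedes all drug: 18 subjects × 1 = 18 tracings. The documents give no rate for a new, clinically significant difference from screening. With an assumed 1% to 5%:

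- 18 × 0.01 = 0.18
- 18 × 0.05 = 0.90

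That is about 0.2 to 0.9 findings in the trial. One subject wrongly placed in or left out of a treatment column moves that treatment's event rate by 1/18 = 5.6 percentage points. The 0.2 to 0.9 covers case C only; the documents give no basis for sizing A or B.

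**The case against.** The strongest reply is that the sentence which actually creates the event refers to baseline, and SAP 6.3.6 defines baseline as the period's pre-dose ECG. Read together, the documents can already yield the right comparator. This stands against one tempting inference, that ECG events are judged against screening instead of the pre-dose tracing. The text does not say that. It names both references and defines neither as the one that prevails. The reply does not remove the conflict, because the only tracing the investigator is expressly told to compare with is the screening one.

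A reader might also infer that a finding seen before dosing simply enters the treatment-emergent table. It does so only through the date wording in SAP 6.3.3.1, against Protocol 9.6.1 and, by onset time, against the assignment rule in SAP 6.3.3. That date wording would affect any Day 1 pre-dose event, not only ECG findings.

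A third inference is that a Period 1 ECG change still present on Day 8 is carried into the other meal state. The documents do not support this. Events are assigned by onset, and seeing an unchanged abnormality again creates neither a new onset nor a worsening.

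Finally, one might count all 36 pre-dose ECGs (18 × 2) as able to show findings that precede the drug. The 18 taken on Day 8 follow dose 1, and a new finding there is a legitimate Period 1 event.

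It is also fair to say that a clinical judgement and a numerical change table may use different references without error. Here, however, the two references sit within a single decision rule.

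**Conclusion.** The point holds as an inconsistency in an operative safety rule. Protocol 6.5.1 gives two comparators, one of them undefined, and they can classify the same post-dose ECG differently in either direction. Separately, a Day 1 pre-dose finding is emergent under the SAP, not emergent under the protocol, and by onset time assigned to no treatment.

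The consequence is minor. It is confined to how ECG adverse events are classified in a descriptive safety summary. Findings before any drug would number about 0.2 to 0.9, which rests wholly on the assumed 1-5% rate in healthy subjects already screened by ECG. The PK analysis does not depend on this rule, and the ECG change-from-baseline tables use the SAP's own baseline. The change is desirable because it is cheap and removes an avoidable source of misclassification. No main conclusion of the trial is at risk.

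**What to change.** - **Protocol 6.5.1:** use one comparator for post-dose ECGs, namely the pre-dose ECG of the same treatment period, as in SAP 6.3.6. Judge each pre-dose ECG against the preceding ECG and record any finding with its true onset time. A new finding on the Day 8 pre-dose ECG then stays with the Period 1 treatment.
- **SAP 6.3.3.1:** define emergence by date and time from administration, to match Protocol 9.6.1. This needs an onset time for events dated Day 1; the assignment rule in SAP 6.3.3 already allows for one.
- **SAP 8.4 and SAP Appendix 1:** state that baseline is taken in each treatment period, as SAP 6.3.6 does.

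The cost is one or two sentences in the protocol, with the IRB/IEC approval that Protocol 10.2 requires for an amendment, and a few words in the SAP. All the ECGs are already scheduled.
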